9.3.2 Non-Serious AE Reporting

Adverse events should be recorded on the AE CRF from the time the patient has signed the informed consent at screening (see Section 8.2) until 30 days after the last dose of study drug. All events should be followed to their resolution, until the Investigator assesses them as stable, irreversible, or until the patient is lost to follow-up, whichever comes first. If a patient begins a new systemic anti-cancer therapy, the AE reporting period for non-SAEs ends at the time the new treatment is started.

All non-serious adverse events should be reported to the Sponsor-Investigator and UCSF, who will report this to Janssen.

9.3.3 UCSF Sponsor-Investigator Reporting Requirements to Regulatory Authorities

Adverse events reporting, including suspected serious unexpected adverse reactions, will be carried out in accordance with applicable local regulations. The Sponsor-Investigator or its designee will be responsible for determining whether or not the suspected adverse reaction meets the criteria for expedited reporting.

For anticipated events reported as individual serious adverse events Janssen will make a determination of relatedness in addition to and independent of the investigator's assessment. Janssen will periodically evaluate the accumulating data and, when there is sufficient evidence and Janssen has determined there is a reasonable possibility that the drug caused a serious anticipated event, they will submit a safety report in narrative format to the investigators and the Study Chair.

Reporting to the UCSF Data and Safety Monitoring Committee

If a death occurs during the treatment phase of the study or within 30 days after the last administration of the study drug(s) and it is determined to be related either to the study drug(s) or to a study procedure, the Investigator or his/her designee must notify the Sponsor-Investigator, who will then notify the DSMC Chair (or qualified alternate) within 1 business day of knowledge of the event. The contact may be by phone or e-mail.

Reporting to the UCSF Institutional Review Board

The Sponsor-Investigator must report events meeting the UCSF IRB definition of "Unanticipated Problem" (UP) within 5 business days of his/her awareness of the event.

Expedited Reporting to the Food and Drug Administration

The Sponsor-Investigator or its designee will be responsible for reporting relevant SAEs to the FDA.

If the study is being conducted under an IND, the Sponsor-Investigator is responsible for determining whether or not the suspected adverse reaction meets the criteria for expedited reporting in accordance with Federal Regulations (21 CFR §312.32).

The Investigator must report in an IND safety report any suspected adverse reaction that is both serious and unexpected. The Sponsor-Investigator needs to ensure that the event meets all three definitions:

- Suspected adverse reaction
- Unexpected
- Serious

If the adverse event does not meet all three of the definitions, it should not be submitted as an expedited IND safety report.

The timeline for submitting an IND safety report to FDA is no later than **15 calendar days** after the Investigator determines that the suspected adverse reaction qualifies for reporting (21 CFR 312.32(c)(1)).

Any unexpected fatal or life-threatening suspected adverse reaction will be reported to FDA no later than **7 calendar days** after the Investigator's initial receipt of the information (21 CFR 312.32(c)(2)).

Any relevant additional information that pertains to a previously submitted IND safety report will be submitted to FDA as a Follow-up IND Safety Report without delay, as soon as the information is available (21 CFR 312.32(d)(2)).

Provide Copies SAE Reporting to Regulatory Authorities to Janssen

Copies of any and all relevant correspondences with regulatory authorities and ethics committees regarding any and all serious adverse events, irrespective of association with

the Janssen Product under study, are to be provided to Janssen within 24 hours of such report or correspondence being sent to applicable regulatory authorities.

10 END OF TREATMENT

A patient may be discontinued from study treatment at any time if the patient or the Investigator feels that it is not in the patient's best interest to continue on study. If a patient's study treatment must be discontinued, this will not result in automatic withdrawal of the patient from the study.

Study treatment with apalutamide will be discontinued for the following reasons, whichever occurs first:

- Disease progression by PCWG criteria. PSA progression is defined as increase of at least 2 ng/mL and 25% above the nadir or baseline on study, whichever is lower, confirmed on repeat measurement at least two weeks later.
- Completion of 13 cycles of study therapy (52 weeks)
- Any episode of seizure
- Any other adverse event that cannot be adequately managed with dose modifications, including dose interruption for treatment-related adverse events that do not improve to Grade 1 or baseline within 14 days, will require study drug discontinuation
- Protocol violation requiring discontinuation of study treatment
- Patient is not compliant with study procedures
- Lost to follow-up
- Patient withdrawal of consent
- Janssen's request for early termination of study

All patients discontinuing study treatment in the absence of disease progression will enter the Post-Treatment Period for PSA monitoring until the time of confirmed PSA progression.

Follow up on study will continue at least the first occurrence of one of the following:

- Disease progression by PCWG criteria.
- Protocol violation requiring discontinuation of study treatment
- Patient is not compliant with study procedures
- Lost to follow-up
- Patient withdrawal of consent
- Janssen's request for early termination of study

If a patient is lost to follow-up, every reasonable effort must be made by the study site personnel to contact the patient and determine the reason for discontinuation/withdrawal. The measures taken to follow up must be documented. When a subject withdraws before completing the study, the reason for withdrawal is to be documented in the CRF and in the source document. Study drug assigned to the withdrawn subject may not be assigned to another subject. Subjects who withdraw will not be replaced.

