11 PROTOCOL VIOLATIONS

A protocol violation occurs when the patient or Investigator fails to adhere to significant protocol requirements affecting the inclusion, exclusion, patient safety and primary endpoint criteria. Protocol violations for this study include, but are not limited to, the following:

- Failure to meet inclusion/exclusion criteria [no waivers will be granted to meet the eligibility criteria]
- Use of a prohibited concomitant medication
- Dose modifications that are not within the protocol specifications
- Any other deviation that presents significant risk or safety concerns to the patient

Failure to comply with Good Clinical Practice (GCP) guidelines will also result in a protocol violation. The Sponsor-Investigator will determine if a protocol violation should result in withdrawal of a patient.

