12.2 ANALYTIC PLAN

12.2.1 Analysis of Primary Endpoint

The primary endpoint for the study is the proportion of patients with undetectable serum PSA (< 0.2 ng/mL) at 6 months following completion of apalutamide therapy (18 months from date of randomization). Fisher's exact test will be used to compare the proportion in the two treatment arms. Patients who discontinue apalutamide prior to completion of 12 months of therapy for reasons other than disease progression by PCWG criteria, as well as patients who withdraw or are lost to follow up, will be considered inevaluable for this analysis. Patients who discontinue treatment for radiographic or clinical progression, even if occurring prior to receipt of SBRT in the experimental arm), would be evaluable for analysis of the primary endpoint.

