12.2.5 Determination of Sample Size

The sample size is based upon the primary endpoint of the study, the proportion of patients with an undetectable serum PSA (< 0.2 ng/mL) 6 months following completion of protocol therapy with apalutamide. Assuming a 10% inevaluable/drop-out rate per treatment arm, a sample size of 60 patients (30 patients/arm) provides 84% power to detect a difference in proportion of patients with undetectable PSA of 25% in the apalutamide + SBRT arm vs. 2.5 % in the apalutamide without SBRT treatment arm, with a unidirectional level of significance of 0.10 using Fisher's exact test.

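### Section 10 both requires PSA monitoring to progression after treatment stops and ends follow-up for a protocol violation or non-compliance; the main cost falls on time to PSA progression

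*Combined protocol and SAP*

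**What the plan says.** Section 10 contains two rules for a man whose apalutamide is stopped without progression.

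- **Follow-up continues.** If study treatment is stopped, "this will not result in automatic withdrawal of the patient from the study". Further on: "All patients discontinuing study treatment in the absence of disease progression will enter the Post-Treatment Period for PSA monitoring", which runs until confirmed PSA progression. Section 4.4 gives the same end-point for follow-up, and Section 7.2.1 schedules PSA every 28 days until then.
- **Follow-up ends.** The next list opens "Follow up on study will continue at least the first occurrence of one of the following". Its second and third bullets are a protocol violation that forces study treatment to stop, and failure to comply with study procedures. Both also appear in the list of reasons for stopping apalutamide.

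Section 11 adds: "The Sponsor-Investigator will determine if a protocol violation should result in withdrawal of a patient". Section 5.2 states that there is no blinding. Section 8.6 ends PSA tracking at progression or when a new non-protocol therapy begins; the second of these is not in the Section 10 follow-up list.

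On analysis, Section 12.2.1 makes two groups inevaluable for the primary endpoint: men who stop apalutamide before 12 months for reasons other than progression, and men who withdraw or are lost. Section 12.2.2 compares time to PSA progression by log-rank test, Kaplan-Meier and Cox model, with no such exclusion.

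**The concern.** A site cannot follow both rules for the same man. If it follows the second, PSA values that could have been obtained at scheduled draws are never collected, and no later analysis can recover them.

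The trigger is loosely defined. Non-compliance has no threshold, the Sponsor-Investigator decides whether a violation leads to withdrawal, and treatment assignment is known. Men removed for conduct may also differ in prognosis from those who stay. If their follow-up simply ends, the time-to-progression analysis treats that censoring as unrelated to outcome, which may not be true. With about 30 men per arm, a few such removals matter.

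**Working it through.** **1. Which men are affected, and in which analysis.** Setting Section 10 beside Sections 11, 12.2.1 and 12.2.2:

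| Situation | PSA under the first rule | PSA under the follow-up list | Primary endpoint as written | Time to PSA progression |
|---|---|---|---|---|
| Apalutamide stopped before 12 months for a violation, no progression | Continues | Ends | Already inevaluable, so no further loss | Later values lost |
| Apalutamide stopped before 12 months for non-compliance, no progression | Continues | Ends | Already inevaluable, so no further loss | Later values lost |
| 52 weeks completed, then removed for non-compliance before month 18 | Continues | Ends | Month-18 PSA lost | Later values lost |
| 52 weeks completed, then withdrawn under Section 11 before month 18 | Continues | Not on the list; follows from the Section 11 decision | Month-18 PSA lost | Later values lost |

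The violation bullet is tied to stopping treatment, so it cannot act once treatment is complete. The direct route to primary-endpoint loss is therefore confined to the last two rows. All four rows affect the secondary endpoint. Section 12.2.2 states no censoring rule; I assume that a man whose draws end is censored at his last PSA.

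**2. The plan's own power figure.** Inputs from Sections 12.2.1 and 12.2.5: "exact test will be used to compare the proportion in the two treatment arms" (Fisher's), "with a unidirectional level of significance of 0.10"; the plan "provides 84% power to detect a difference in proportion of patients with undetectable PSA of 25% in the apalutamide + SBRT arm" against "2.5 % in the apalutamide without SBRT treatment arm"; 30 per arm with 10% inevaluable.

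- Evaluable per arm: 30 × (1 − 0.10) = 27.
- One-sided Fisher p for x₁ SBRT and x₂ control responders: P(X ≥ x₁), with X hypergeometric (2n men in total, x₁ + x₂ responders, n in the SBRT arm).
- Power = Σ Bin(x₁; n, 0.25) · Bin(x₂; n, 0.025) over all pairs with p ≤ 0.10.
- At n = 27 this gives 83.6%, which reproduces the stated 84%.

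**3. What further losses would cost.** The documents do not say how many men these rules would remove. Purely as a range, for losses beyond the planned 10% and equal in both arms:

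| Evaluable per arm | Power | Change from row above |
|---|---|---|
| 27 | 83.6% | n/a |
| 26 | 81.9% | −1.7 points |
| 25 | 80.0% | −1.9 points |
| 24 | 77.8% | −2.2 points |

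At 21, 24, 27 or 30 per arm, significance needs 4 SBRT responders if there are no control responders, and 5 if there is one. For example, at 27 per arm with no control responders, 4 responders give p = C(27,4)/C(54,4) = 17,550/316,251 = 0.055, and 3 give p = 2,925/24,804 = 0.118.

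These figures concern the primary endpoint. The documents give no event-rate assumption for the comparison of time to PSA progression, so the cost there cannot be put into numbers.

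**The case against.** The strongest objection is that the primary analysis hardly depends on this. A reader might infer that every man stopped for a violation or non-compliance is a primary-endpoint value lost through Section 10. The documents do not support that. Section 12.2.1 already excludes non-progressing men who stop before 12 months, whether or not PSA is drawn later, so deleting the two bullets returns none of them to that analysis. This objection stands in full. The remaining window runs from week 52 to month 18. In it the scheduled contacts are little more than PSA draws and a 30-day safety check, so a man judged non-compliant there may be missing PSA values anyway.

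A reader might also take the fall from 87.9% power at 30 per arm to 83.6% at 27, or 4.3 points, as the size of this defect. It is the cost of the plan's whole 10% allowance for all causes and is already inside the stated 84%. Likewise, one responder can tip any Fisher test at its boundary, whatever the reason for the missing value.

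Nothing in the documents shows that removals would differ by arm. Section 11 names who decides on violations, but no text names who judges non-compliance. Bias is possible, not demonstrated.

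Finally, the lead-in sentence is incomplete, and the words at least could be read as setting a minimum. That softens the conflict without removing it: a site permitted to stop at that event would still be at odds with the rule that all such men enter monitoring until progression.

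**Conclusion.** The contradiction is real and should be corrected. Its main consequence is for time to PSA progression, where men taken off follow-up for conduct reasons would be censored, possibly informatively, although their draws are scheduled. That rests on censoring at the last PSA, which the plan does not state. The effect on the primary endpoint is narrow: men who finish 52 weeks and are removed for non-compliance, or withdrawn under Section 11, before month 18. No count of affected men is available, so the range from 83.6% to 77.8% (27 down to 24 per arm) illustrates sensitivity and does not estimate the loss. It assumes the design rates of 25% and 2.5% hold among the men who remain.

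**What to change.** 1. In Section 10, delete the second and third bullets (violation and non-compliance) from the follow-up list and complete the lead-in sentence.
2. In Section 11, limit the Sponsor-Investigator's withdrawal decision to study treatment.
3. State that the scheduled 28-day PSA draws continue until confirmed PSA progression, withdrawal of consent for follow-up, death, loss to follow-up or study termination.
4. Reconcile Sections 4.4, 8.6, 10 and 11, including the new-therapy stop that appears only in Section 8.6.

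The cost is an amendment to wording and some additional PSA draws, already in the schedule, in men who have stopped treatment. A requirement for PSA at month 18 in every randomised man would go further: Sections 4.4, 7.2.1 and 8.6 end draws at progression, and Section 8.6 also at new therapy, so those later draws are not all scheduled now. Using early stoppers' month-18 PSA in the primary analysis would need a separate change to Section 12.2.1.

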11 PROTOCOL VIOLATIONS

A protocol violation occurs when the patient or Investigator fails to adhere to significant protocol requirements affecting the inclusion, exclusion, patient safety and primary endpoint criteria. Protocol violations for this study include, but are not limited to, the following:

- Failure to meet inclusion/exclusion criteria [no waivers will be granted to meet the eligibility criteria]
- Use of a prohibited concomitant medication
- Dose modifications that are not within the protocol specifications
- Any other deviation that presents significant risk or safety concerns to the patient

Failure to comply with Good Clinical Practice (GCP) guidelines will also result in a protocol violation. The Sponsor-Investigator will determine if a protocol violation should result in withdrawal of a patient.

12 STATISTICAL METHODS AND CONSIDERATIONS

12.1 ANALYSIS POPULATIONS

Safety Analysis Population [SAFETY]: All patients who receive at least one dose of study drug, with treatment assignments designated according to actual study treatment received will be the primary population for evaluating safety and treatment compliance and administration.

12.2 ANALYTIC PLAN

12.2.1 Analysis of Primary Endpoint

The primary endpoint for the study is the proportion of patients with undetectable serum PSA (< 0.2 ng/mL) at 6 months following completion of apalutamide therapy (18 months from date of randomization). Fisher's exact test will be used to compare the proportion in the two treatment arms. Patients who discontinue apalutamide prior to completion of 12 months of therapy for reasons other than disease progression by PCWG criteria, as well as patients who withdraw or are lost to follow up, will be considered inevaluable for this analysis. Patients who discontinue treatment for radiographic or clinical progression, even if occurring prior to receipt of SBRT in the experimental arm), would be evaluable for analysis of the primary endpoint.

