Primary Endpoint	
 ▪ Proportion of patients with undetectable serum PSA (< 0.2 ng/mL) at 6 months following completion of apalutamide therapy (18 months from date of randomization).
Secondary Endpoints	
 1. Time to PSA progression by PCWG criteria 2. Feasibility and Safety of apalutamide and concurrent SBRT
Exploratory Endpoints	
 1. Association between genomic factors and presence of oligometastatic disease 2. Association between somatic and germline genomic alterations with clinical outcomes Note: The italicized objectives above were discontinued in Protocol v. 8.0. See Section 7.3 for additional information. 3. Association between baseline PSMA-PET scan uptake and distribution of lesions with treatment outcomes.
Statistical Analysis/ Sample Size Justification	The primary efficacy is based on the primary endpoint of the study, the proportion of patients with undetectable PSA (PSA < 0.2 ng/mL) 6 months following completion of 12 months of apalutamide therapy (18 months from date of randomization). Assuming a 10% inevaluable/drop-out rate per treatment arm, a sample size of 60 patients (30 patients/arm) provides 84% power to detect a difference in proportion of patients with undetectable PSA of 25% in the apalutamide + SBRT arm vs. 2.5 % in the apalutamide monotherapy arm, with a unidirectional level of significance of 0.10 (Fisher's exact test). Patients who discontinue apalutamide prior to completion of 12 months of therapy for reasons other than disease progression by PCWG criteria will be considered inevaluable for this analysis.

List of Abbreviations

AE	adverse event
ALP	alkaline phosphatase
ALT	alanine aminotransferase
ANC	absolute neutrophil count
AST	aspartate aminotransferase
BUN	blood urea nitrogen
CBC	complete blood cell (count)
CR	complete response
CRC	Clinical Research Coordinator
CRF	case report form
CT	computerized tomography
CTCEA	Common Terminology Criteria for Adverse Events
CTEP	Cancer Therapy Evaluation Program
CTMS	Clinical Trial Management System
CTV	clinical tumor volume
DFS	disease-free survival
DLT	dose limiting toxicity
DSMC	Data and Safety Monitoring Committee
DSMP	Data and Safety Monitoring Plan
ECOG	Eastern Cooperative Oncology Group
FCBP	female of childbearing potential
FDA	Food and Drug Administration
GCP	Good Clinical Practice
HBV	hepatitis B virus
HCT	hematocrit
HCV	hepatitis C virus

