However the optimal duration of apalutamide therapy in this setting has not been determined. Extrapolation from other studies evaluating the use of AR targeted therapy in hormone-naïve prostate cancer patients with recurrent, but non-extensive disease suggests that the approach selected is appropriate. Clinical trials testing AR targeted therapy in conjunction with “salvage” radiotherapy in men with progressive disease following prostatectomy have utilized AR targeted therapy from 6 months (Carrie et al, Lancet Oncol 2016) to 24 months (Shipley et al, NEJM, 2017.) Furthermore, in a trial of intermittent androgen deprivation in patients with non-metastatic disease progression following radiation therapy, one year of systemic therapy was used (Crook et al, NEJM, 2012). One year of apalutamide therapy will therefore be used in both arms. Shorter duration is felt inadequate for patients with potentially metastatic disease, whereas longer duration would delay read out of results.

Although SBRT is an appropriate therapeutic approach in selected patients with oligometastatic prostate cancer, its utility has not been rigorously demonstrated. It is hypothesized that the addition of SBRT to apalutamide will result in clinically meaningful benefit, with improvement in time to subsequent metastasis, and potentially in an overall survival benefit. However, before embarking on a large phase 3 trial, an intermediate signal of activity is required. Only a very small proportion (2.5%) of patients with non-metastatic CRPC treated with apalutamide alone reach a serum PSA level of < 0.2 ng/mL. A nadir PSA of < 0.2 ng/mL has previously been shown to be strongly associated with long-term survival, and therefore represents a reasonable intermediate endpoint for a randomized phase 2 study. Positive results from the current study would form the strong justification for a follow-on randomized phase 3 study to investigate whether addition of SBRT impacts long-term treatment outcomes including radiographic progression-free and overall survival.

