12.2.4 Interim Analysis

No interim analysis will be performed, as the primary endpoint (PSA undetectable rate 6 months following completion of protocol treatment) will not be evaluable until after all patients have been accrued on study.

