13.3 INSTITUTIONAL REVIEW BOARD APPROVAL

The protocol, the proposed informed consent form, and all forms of participant information related to the study (e.g., advertisements used to recruit participants) will be reviewed and approved by the UCSF Institutional Review Board or the IRB of the participating site. For UCSF, prior to obtaining IRB approval, the protocol must be approved by the Helen Diller Family Comprehensive Cancer Center Site Committee and by the Protocol Review Committee (PRC). The initial protocol and all protocol amendments must be approved by each respective IRB prior to implementation.

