13.5 CHANGES IN THE PROTOCOL

Once the protocol has been approved by the UCSF IRB, any changes to the protocol must be documented in the form of an amendment. The amendment must be signed by the Investigator and approved by PRC and the IRB prior to implementation.

If it becomes necessary to alter the protocol to eliminate an immediate hazard to patients, an amendment may be implemented prior to IRB approval. In this circumstance, however, the Investigator must then notify the IRB in writing within five (5) working days after implementation.

The Study Chair and the UCSF study team will be responsible for updating any participating sites.

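### An optional, low-cost gain: at the same one-sided 0.10, Boschloo's exact test would raise primary-test power from 83.6% to 88.0% at 27 evaluable per arm

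*Combined protocol and SAP*

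**What the plan says.** Section 12.2.1 names the primary test: Fisher's "exact test will be used to compare the proportion in the two treatment arms". That section gives neither the significance level nor the direction of the test. Both come from section 12.2.5 and the abstract, where the 2.5% is placed "in the apalutamide monotherapy arm, with a unidirectional level of significance of 0.10".

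Section 12.2.5 sets the size of the trial: "Assuming a 10% inevaluable/drop-out rate per treatment arm, a sample size of 60 patients (30 patients/arm") which "provides 84% power to detect a difference in proportion of patients with undetectable PSA of 25"% with SBRT against 2.5% without. Section 12.2.4 adds: "No interim analysis will be performed, as the primary endpoint" will not be available until accrual is complete. The whole 0.10 is therefore available for one final test.

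Section 3.1 says what a positive result would be used for: "Positive results from the current study would form the strong justification for a follow-on randomized phase 3 study". No unconditional exact test is mentioned anywhere in the document.

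**The concern.** Fisher's test conditions on the total number of responders. When that total is small, few p-values are possible, and the largest attainable one below 0.10 is often well below it. The expected total here is 27 × (0.25 + 0.025) = 7.4 responders, so much of the allowed error rate cannot be spent.

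Boschloo's test takes Fisher's p-value as its statistic. It then sets the cutoff so that the rejection probability, maximised over every possible common response rate, stays at or below 0.10. It is therefore valid at the same level, and it can never reject less often than Fisher.

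What is at stake is power that the sponsor could have without another patient, visit or sample. The plan as written remains valid.

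**Working it through.** **Inputs.** 30 patients per arm, 10% inevaluable, 25% versus 2.5%, one-sided 0.10, Fisher's exact test (12.2.5 and abstract); no interim look (12.2.4). Evaluable per arm: 30 × 0.9 = 27. The document does not print the 27.

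**Method.** Let x be responders with SBRT and y responders without. For each table (x, y):

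- Fisher one-sided p = P(X ≥ x), with X hypergeometric given the total x + y.
- Power = Σ Bin(x; n₁, 0.25) × Bin(y; n₂, 0.025) over the rejected tables.
- Size = the same sum with one common rate π in both arms, maximised over a fine grid of π between 0 and 1.
- Boschloo rejects when Fisher's p ≤ c, where c is the largest cutoff with maximum size ≤ 0.10.

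**Step 1: the plan's own figure.** At 27/27 Fisher rejects from 4 vs 0, 5 vs 1, 7 vs 2, 8 vs 3 and 10 vs 4 upward. Power is 0.8363, which reproduces the stated 84%. Maximum size is 0.0668, at π = 0.50.

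**Step 2: Boschloo at the same level.** The cutoff is c = 0.1355; the next possible cutoff, 0.1375, would have size 0.1025. It rejects from 3 vs 0, 5 vs 1, 6 vs 2, 8 vs 3 and 9 vs 4 upward. Maximum size is 0.0966, at π = 0.367. Power is 0.8799, a gain of 0.8799 − 0.8363 = 0.0436.

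**Step 3: where the gain comes from.**

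| Added table | Fisher p | Boschloo p | Added power |
|---|---|---|---|
| 3 vs 0 | 0.118 | 0.070 | 0.0231 |
| 6 vs 2 | 0.125 | 0.079 | 0.0200 |
| 9 vs 4 | 0.101 | – | 0.0004 |

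As a hand check, Fisher's p for 3 vs 0 is C(27,3)/C(54,3) = 2925/24804 = 0.118. Taking 3 vs 0 out of the Boschloo region leaves power 0.8568, a gain of 2.1 points.

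**Step 4: what Fisher would need.** Fisher power is 85.2% at 28 evaluable per arm, 86.6% at 29 and 87.9% at 30. Since 30/0.9 = 33.3, that means 34 randomised per arm, or 68 in all.

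**Step 5: other arm sizes** (25% vs 2.5%). Fisher's rejection set lay inside Boschloo's at every pair.

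| SBRT/control evaluable | Fisher | Boschloo |
|---|---|---|
| 30/30 | 87.9% | 91.2% |
| 24/24 | 77.8% | 84.0% |
| 21/21 | 69.8% | 78.3% |
| 26/28 | 81.0% | 86.3% |
| 28/26 | 81.3% | 88.1% |
| 30/24 | 84.3% | 86.2% |
| 24/30 | 81.2% | 88.9% |

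**Step 6: other assumed rates at 27/27.** 20% vs 2.5%: 67.8% to 75.4%. 25% vs 5%: 70.4% to 76.2%. 25% vs 10%: 44.0% to 50.8%.

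**Step 7: false-positive rate at 27/27, Fisher then Boschloo.** Both arms at 2.5%: 0.2% and 1.5%. At 5%: 1.5% and 4.2%. At 10%: 4.3% and 6.5%. Maximum over all rates: 6.7% and 9.7%.

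**The case against.** The plan names a valid exact test and states its power correctly, so preferring Fisher is a legitimate choice. The gain is largely a lower bar of evidence: 2.31 + 2.00 = 4.31 of the 4.36 points come from accepting 3 vs 0 and 6 vs 2, and three responders against none is thin support for a phase 3 trial. At the sponsor's own control rate the false-positive rate rises about sixfold (0.24% to 1.49%). All of this is true. It stays within the 10% limit that the sponsor set, but it is a reason for the sponsor to decide deliberately.

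The gain also depends on the final split of evaluable patients. At 30/24 it is only 1.9 points and 3 vs 0 is still not rejected; at 24/30 it is 7.7 points and Fisher itself already rejects 3 vs 0. This qualifies the size of the gain. Boschloo was never less powerful and never exceeded 10% at the splits examined, and the 88% is a planning figure at 27/27 just as the 84% is.

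Two further cautions stand. The larger gains at 24/24 and 21/21 assume that loss is unrelated to outcome; section 12.2.1 excludes some patients on post-randomisation events, and a change of test does not address that. And the trial is open-label with PSA measured every cycle (sections 5.2 and 7.2.1), so a late move to a more liberal test could look chosen after the fact. The document cannot show whether arm-level results have been seen.

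**Conclusion.** The point holds as a cheap improvement, not as an error. Under the sponsor's own assumptions (25% vs 2.5%, 27 evaluable per arm, one-sided 0.10), Boschloo's test has 88.0% power against 83.6% for Fisher, with maximum size 9.7% against 6.7%. The gain is larger if both arms lose more than 10%: 6.2 points at 24/24 and 8.5 points at 21/21. The 88% rests on the same response rates as the 84%, and the change of test gives no protection if those rates are wrong. Whether the change is worth making turns on two things the document does not settle: whether the sponsor would act on 3 vs 0, and whether the decision can be shown to precede any comparison of outcomes between arms.

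**What to change.** 1. Decide first whether 3 vs 0 responders would be acted on. If not, keep Fisher as the primary test.
2. If so, amend 12.2.1, 12.2.5 and the abstract to name Boschloo's exact test, one-sided 0.10, for a higher proportion in the apalutamide + SBRT arm. This would also put the level and direction into 12.2.1, where they are now absent.
3. Restate power as about 88% at 27 evaluable per arm under the same rates and 10% loss, and show how it varies with unequal evaluable numbers.
4. Keep Fisher's test as a sensitivity analysis.
5. Document that the amendment was made before any between-arm outcome comparison. If that cannot be shown, leave Fisher primary and report Boschloo as supportive.
6. Specify the software call. In scipy's `boschloo_exact` the arms must be the table columns: 3 vs 0 at 27/27 then gives p = 0.070, whereas arms as rows gives 0.061.

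**Cost.** No added patients or data, and a few lines of code. An amendment is needed: under 13.5, "The amendment must be signed by the Investigator and approved by PRC and the IRB prior to implementation", and under 13.3, "The initial protocol and all protocol amendments must be approved by each respective IRB prior to implementation". The other costs are a less familiar test, rejection at smaller responder counts, and a higher false-positive rate within the 10% limit.
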